### **Expedited Reporting by Investigator to Celgene**

For the purpose of regulatory reporting, Celgene Drug Safety will determine the expectedness of events of being related to lenalidomide based on the Investigator Brochure. In the United States, all suspected unexpected serious adverse reactions (SUSARs) will be reported in an expedited manner in accordance with 21 CFR 312.32.

Serious adverse events (SAE) are defined in Section 17.2.1. The investigator must inform Celgene in writing using a Celgene SAE form of any SAE within 24 hours of being aware of the event. The written report must be completed and supplied to Celgene by facsimile within 24-hours/1 business day. The initial report must be as complete as possible, including an assessment of the causal relationship between the event and the investigational product(s). Information not available at the time of the initial report (e.g., an end date for the adverse event or laboratory values received after the report) must be documented on a follow-up report. A final report to document resolution of the SAE is required. The Celgene tracking number (RV-NHL-PI-637) and the institutional protocol number should be included on SAE reports (or on the fax cover letter) sent to Celgene. A copy of the fax transmission confirmation of the SAE report to Celgene should be attached to the SAE and retained with the patient records.

### **Investigator Reporting to the FDA**

**Serious** adverse events (SAEs) that are **unlisted/unexpected, and at least possibly associated to the drug**, and that have not previously been reported in the Investigators brochure, or reference safety information document should be reported promptly to the MSK IND office in order to contact the Food and Drug Administration (FDA) by telephone or by fax. Fatal or life threatening SAEs that meet the criteria for reporting to the FDA will be reported to the FDA within 7 calendar days after awareness of the event. All other SAEs that meet the criteria for reporting to the FDA must be reported to the FDA within 15 calendar days after awareness of the event by the IND office at MSK. A clear description of the suspected reaction should be provided along with an assessment as to whether the event is drug or disease related.

### **Adverse Event Updates/IND Safety Reports**

Celgene shall notify the Investigator via an IND Safety Report of the following information:

- Any AE associated with the use of drug in this study or in other studies that is both serious and unexpected.
- Any finding from tests in laboratory animals that suggests a significant risk for human subjects including reports of mutagenicity, teratogenicity, or carcinogenicity.

The Investigator shall notify his/her IRB/EC promptly of these new serious and unexpected AE(s) or significant risks to subjects.

The Investigator must keep copies of all AE information, including correspondence with Celgene and the IRB/EC, on file (see records retention information).

### **17.3 SAE Reporting for Participating Sites**

#### Responsibility of Participating Sites

- Participating sites are responsible for reporting all SAEs to their site IRB per local guidelines. Site IRB approvals/acknowledgments must be sent to MSK upon receipt. .
- Participating sites are responsible for submitting the SAE Report form to MSK within 3 calendar days of learning of the event.
- When a death is unforeseen and indicates participants or others are at increased risk of harm, participating sites should notify the MSK PI as soon as possible but within 24 hours of the time the site becomes aware of the event.

### Responsibilities of MSK

- MSK is responsible for submitting all SAEs to the MSK IRB/PB and funding entities (if applicable) as described in the protocol.
- MSK is responsible for informing all participating sites about all unexpected SAEs that are either possibly, probably, or definitely related to the study intervention within 15 days of receiving the stamped SAE report from the MSK IRB/PB.
- MSK is responsible for informing all participating sites within 24 hours or on the next business day about a death that is unforeseen and indicates participants or others are at increased risk of harm.

### **17.4 Communication of DLTs**

For the purposes of this clinical trial, A DLT is defined as non-hematologic toxicity of grade  $\geq 3$  (attributed to study drug) and hematologic grade 4 (attributed to study drug) toxicity defined as grade 4 thrombocytopenia of any duration, failure of recovery of absolute neutrophil count  $\geq 1.0$  K/ $\mu$ L or platelets to  $\geq 50$  K/ $\mu$ L within 14 days of last treatment; or inability to receive day 1 of cycle 2 due to continued drug-related toxicity from the cycle. During the course of the Phase Ib portion of this study, all DLTs that occur will be immediately communicated via email to each participating site/investigator. Additionally, routine conference calls will be conducted with all participating sites to communicate all safety issues including DLTs. The frequency of these conference calls will be determined by enrollment rate of the trial. Lastly, all events that qualify as SAEs should be reported according to the protocol guidelines.

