## 4.0 OVERVIEW OF STUDY DESIGN/INTERVENTION

### 4.1 Design

**Phase Ib:** The phase Ib portion of the study is designed to determine the MTD of romidepsin and lenalidomide. All patients must have a relapsed or refractory B-cell lymphoma, T-cell lymphoma, or multiple myeloma. Patients will be treated on a 28-day cycle with romidepsin infused on day 1, 8, and 15, and lenalidomide taken orally on days 1-21. The design is a standard 3+3 dose escalation (Table 1) of romidepsin and lenalidomide. The first cohort will enter at dose level 1.

Dose Level	Romidepsin	Lenalidomide
-1	8 mg/m 	10 mg
1	8 mg/m 	15 mg
2	8 mg/m 	25 mg
3	10 mg/m 	25 mg
4	14 mg/m 	25 mg

Table 1: Description of dose level

DLT is defined in cycle 1 (in phase Ib).

Definitions:

- Grade  $\geq$  3 non-hematologic (attributed to study drugs)
- Grade 4 hematologic toxicities (attributed to study drugs) defined as:
  - Grade 4 thrombocytopenia (platelets  $< 25$  K/ $\mu$ L)
  - Grade 4 neutropenia (absolute neutrophil count (ANC)  $< 0.5$ )
- Grade 3 thrombocytopenia or neutropenia that results in a  $> 3$  day delay in any romidepsin dose in cycle 1.
- One week or greater delay in initiating cycle 2 day 1 due to continued drug-related toxicity.

Any patient with an adverse event that meets the DLT definition is considered evaluable for MTD determination. Patients who do not have a DLT, but received  $<3$  doses of romidepsin or  $<80\%$  (17/21) of the doses of lenalidomide during cycle 1 will not be evaluable for MTD and will be replaced.

Three patients will be initially treated in each cohort until the MTD is determined. If dose level 4 (full dose of each drug) is achieved without DLT after 1 cycle that dose level will be deemed the optimal dose and the study will proceed to a phase IIa expansion cohort. Patients treated at MTD in the phase Ib portion will be counted towards the phase IIa accrual by disease subtype and also for all efficacy and toxicity endpoints unless they did not have measurable disease at point of study entry as allowed in the phase Ib portion.

**Phase IIa:** The phase IIa portion will further assess the toxicity and safety and allow a preliminary assessment of the efficacy of the combination to provide background for a potential future subtype specific phase II study (see Section14.0).

DLT is defined in cycles 1-4 (in phase IIa)

Definitions:

- Grade  $\geq$  3 non-hematologic (attributed to study drugs)

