- Grade 4 hematologic toxicities (attributed to study drugs) defined as:
  - Grade 4 thrombocytopenia (platelets  $< 25$  K/ $\mu$ L)
  - Grade 4 neutropenia (absolute neutrophil count (ANC)  $< 0.5$ )
- Grade 3 thrombocytopenia or neutropenia that results in a  $> 4$  day delay in any romidepsin dose in cycle 1.
- One week or greater delay in initiating cycle 2 day 1 due to continued drug-related toxicity.

At the time of enrollment the patients will be identified as representing three cohorts based upon disease subtype: 1) B-cell lymphoma 2) multiple myeloma 3) PTCL. Each disease specific cohort will enroll 15 patients. We plan to accrue 38 patients into the phase IIa portion including those treated at the MTD of the phase Ib portion. The assessment of toxicity and efficacy will be performed within the entire cohort evaluable at MTD. A preplanned exploratory analysis of the toxicity and efficacy of the disease specific cohorts will also be performed. Efficacy measures which will be determined include ORR, CBr (for myeloma), TTR, DOR, and EFS. ORR is defined as the percentage of patients achieving a best response of CR/CRu, very good partial response (VGPR--myeloma only), or PR at any disease assessment time point. CBr is defined as CR, VGPR, PR or MR (minimal response) in myeloma patients. TTR is defined as the time or number of cycles between study registration and documentation of first response (CR/Cru, VGPR, or PR). DOR is defined as the time or number of cycles between documentation of first response and progression, change of therapy, death, or date of last contact (if still alive without progression). EFS is defined as the time between study registration and documented progression, change in therapy, or death if no progression was observed.

[figure not shown]

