**Table 2: Description of dose level.**

If all three patients complete one cycle of therapy without a DLT at the respective dose level then the subsequent dose level can be accrued. A DLT is defined in section 4.1. After the MTD is determined by either DLT or accrual of six patients without DLT at dose level 4 in the first cycle accrual to the phase Ib portion will be considered closed. The MTD from the phase Ib study will be used for the initial starting doses for both romidepsin and lenalidomide. The treatment plan is described below for the phase Ib portion:

Romidepsin/Lenalidomide Cycle 1 Day 1

Romidepsin IVPB over 4 hours

Lenalidomide PO q days 1-21

Romidepsin/Lenalidomide Cycle 1 Day 8

Romidepsin IVPB over 4 hours

Romidepsin/Lenalidomide Cycle 1 Day 15

Romidepsin IVPB over 4 hours

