## **9.7 Dose Continuation, Modification and Interruption**

Subjects will be evaluated for AEs at each visit with the NCI CTCAE v4.0 (Appendix H): NCI CTCAE v4.0) used as a guide for the grading of severity. DLTs as defined will be tabulated in cycle 1 of the phase Ia and cycles 1-4 of the phase IIa portion of the study. The toxicity decision rule for the IIa portion is described in Section 14.0. The sections below describe dose reduction steps, instructions for initiation of a new cycle of therapy and dose modifications during a cycle of therapy. Inability to meet treatment criteria will result in holding the dose.

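### DLT is defined differently in sections 4.1 and 17.4, section 14 and the myeloma rule do not settle which phase IIa list applies, and scoring of an omitted romidepsin dose is not stated

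*Combined protocol and SAP*

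**What the plan says.** Section 4.1 gives two DLT lists, one for phase Ib (cycle 1) and one for phase IIa (cycles 1-4). Both count attributed grade 4 neutropenia outright, in the item beginning "Grade 4 neutropenia (absolute neutrophil count (ANC", with a cut-off of 0.5 and no duration condition. Both count grade 3 thrombocytopenia or neutropenia that causes a "day delay in any romidepsin dose in cycle 1", but the delay must exceed 3 days in phase Ib and 4 days in phase IIa. Both count a delay of a week or more in starting cycle 2.

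Section 9.2 says "A DLT is defined in section 4.1", and section 14 cites 4.1 for escalation. For phase IIa monitoring, section 14 instead applies the phase Ib DLT over cycles 1-4. Section 9.7 says "DLTs as defined will be tabulated in cycle 1 of the phase Ia and cycles 1-4 of the phase IIa portion of the study" (phase Ia evidently means phase Ib). The myeloma rule in 9.3 lowers the starting dose after two DLTs in six or fewer patients and cites no definition.

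Section 17.4 begins "For the purposes of this clinical trial, A DLT is defined as non-hematologic toxicity of grade" 3 or above and continues with its own list. During phase Ib, "all DLTs that occur will be immediately communicated via email to each participating site/investigator".

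On evaluability, 4.1 says "Any patient with an adverse event that meets the DLT definition is considered evaluable for MTD determination". A phase Ib patient with no DLT and fewer than three romidepsin doses, or under 80% "of the doses of lenalidomide during cycle 1 will not be evaluable for MTD and will be replaced".

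**The concern.** Every safety decision in this trial is a count of patients with a DLT: the 3+3 escalation, the phase IIa boundaries (8 of 15, 16 of 30, more than 24 of 45) and the myeloma two-in-six rule. If sections list different events, two sites can classify the same patient differently while each follows the protocol.

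Three things are at stake. Sites that recognise and report DLTs from 17.4 may miss events that 4.1 counts. The phase IIa and myeloma counts operate after the MTD is set, and the text does not settle which 4.1 list feeds them. Finally, a patient whose only event is a romidepsin dose omitted for grade 3 cytopenia could be scored as a DLT or, in phase Ib, be replaced and leave the denominator.

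**Working it through.** **1. The lists side by side**

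| Item | 4.1 phase Ib | 4.1 phase IIa | 17.4 |
|---|---|---|---|
| Attributed non-hematologic | grade 3 or above | same | same |
| Grade 4 thrombocytopenia | counts | counts | counts |
| Grade 4 neutropenia | counts outright | counts outright | not named; counts if ANC fails to reach 1.0 K/µL within 14 days of last treatment (parallel platelet item at 50 K/µL) |
| Grade 3 cytopenia delaying romidepsin in cycle 1 | more than 3 days | more than 4 days | absent |
| Cycle 2 day 1 | a week or more late | a week or more late | could not be given; no length stated |
| Window | cycle 1 | cycles 1-4 | none stated |

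Grade 4 neutropenia that recovers within the 14 days is a DLT in 4.1 but not on 17.4's neutrophil wording. Grade 3 neutropenia with a qualifying romidepsin delay is on both 4.1 lists and not in 17.4. A cycle 2 start only a few days late is not a DLT in 4.1, but could be one in 17.4.

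**2. Which list feeds phase IIa**

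Section 14 points to the first column, with the window extended to cycles 1-4. Section 4.1 supplies the second column. Section 9.3 points to neither. Apart from the window, the two columns differ in one threshold.

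**3. Delay and omission**

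Table 5 and the Table 7 legend allow romidepsin at most 3 days late, and omitted doses are not made up (9.7.1, Table 5). A hold beyond that limit therefore normally ends as an omission. The delay items speak only of delay.

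**4. The plan's own figures**

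Escalation probability is (1-p)^3 + 3p(1-p)^5. At p = 20%, 25% and 30% it gives 0.709, 0.600 and 0.494, against 0.71, 0.60 and 0.49 in section 14; the other five entries also reproduce.

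The exact sequential binomial for at least 8 of 15, at least 16 of 30 and more than 24 of 45 gives 0.004, 0.018, 0.052, 0.122 and 0.241 at 20%, 25%, 30%, 35% and 40%. The stated values are 0.004, 0.016, 0.056, 0.118 and 0.243. At 50% it gives 0.607 against 0.632, which has no bearing here.

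For the myeloma rule, P(X ≥ 2) with X ~ Bin(6, p) is 0.345, 0.466 and 0.580 at 20%, 25% and 30%.

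The tables take the DLT rate as given. The definition decides which rate applies, and the documents give no rate under any of the lists.

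**5. Direction of the omission question in phase Ib**

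Let p be the share of patients with another DLT and q the share whose only event is such an omission. If omissions count, the rate is p + q. If those patients are replaced, it is p/(1-q). The difference is q(1-p-q)/(1-q), which is positive when q > 0 and p + q < 1, so replacement biases the rate downward.

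As an illustration only, assume p = 0.20:

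- q = 0.05: the rate is 0.25 counted and 0.20/0.95 = 0.211 replaced; escalation probability is 0.600 against 0.686.
- q = 0.10: the rate is 0.30 counted and 0.20/0.90 = 0.222 replaced; escalation probability is 0.494 against 0.660.

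These values of p and q are assumptions. The example says nothing about the size of the 4.1 and 17.4 conflict.

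**The case against.** The strongest reply is that 4.1 governs: 9.2 and 14 cite it for escalation, no decision rule cites 17.4, and the e-mail duty in 17.4 covers phase Ib only. That stands. A reader might infer that escalation ran on 17.4 and that the declared lymphoma MTD is therefore wrong. The documents do not support this. What remains is that 17.4 is worded as a trial-wide definition and sits where sites look when reporting. One could read its reference to hematologic grade 4 toxicity as covering neutropenia, but it then defines that term by a list that does not name it.

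The conflict between 14 and 4.1 can also be called a one-day difference with little reach. A reader might offer a day-15 dose given on day 19, inside the day-21 limit, as a DLT on one list only (19 - 15 = 4 days). That dose falls outside the 3-day limit in Table 5 and the Table 7 legend, so it is not a permitted administration. Within the limit, neither delay item is met. The contradiction remains on paper, and its practical effect depends largely on how an omission is scored.

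A reader might see the cycle 1 and cycle 2 day 1 ties as contradicting a cycles 1-4 window. They need not: grade-based items can run for four cycles while delay items carry a narrower window. This needs clarification.

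The myeloma rule sits in the phase IIa plan, so 4.1's phase IIa list and the window in 9.7 may apply by default. The section 14 pointer to phase Ib leaves that open.

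On omissions, the natural reading is that they meet the delay item, since 10.2 describes unmet blood criteria as a reason to delay. The patient is then a DLT and evaluable. No passage reports a patient replaced for this reason.

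**Conclusion.** The inconsistency is real and worth correcting. Section 17.4 and section 4.1 classify some patients differently, section 14 and section 4.1 name different lists for phase IIa, and the myeloma rule names none. These conclusions rest on the text alone and need no assumed rates. The scoring of an omitted dose is a smaller gap: the direction of bias under the unfavourable reading is certain, but whether anyone used that reading is unknown.

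The size of the effect cannot be computed from the documents. The escalation gap of 0.086 to 0.166 (0.686 - 0.600 and 0.660 - 0.494) holds only for the assumed 20% and 5-10% rates, and only if omissions were scored as no DLT. No figure is available for the 4.1 and 17.4 difference or for the 3-day and 4-day thresholds. Nothing here shows that the declared MTD is wrong.

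**What to change.** Reconcile sections 4.1, 14, 17.4 and 9.3 to one DLT definition per phase, state it once and cross-reference it elsewhere, including in the myeloma rule. Add a sentence on how a romidepsin dose omitted for toxicity is scored, and another on whether the delay items apply beyond cycle 1 and cycle 2 day 1. Then re-check the recorded events, including those of any replaced phase Ib patient, against the reconciled text. Which list, thresholds and window apply is a clinical decision for the investigators.

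The cost is amendment wording and one review of recorded events. No new patients or procedures are needed.

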### **17.5 Safety Reports**

MSK must submit outside safety reports to the MSK IRB/PB according to institutional guidelines. All outside safety reports will be made available to the participating sites. Outside safety reports that are reportable to the MSK IRB/PB will be distributed to the participating sites immediately upon receiving a stamped copy from the MSK IRB/PB. Participating sites will receive a special alert for any outside safety reports that warrant a significant change to the conduct of the study.

Outside safety reports that are not reportable to the MSK IRB/PB, will be sent to the participating sites monthly.

Participating sites are responsible for submitting safety reports to their site IRB per their local guidelines. All site IRB approvals/acknowledgments of safety reports must be sent to MSK upon receipt.

#### **17.5.1 Unanticipated Problems**

Unanticipated problems involving risks to participants or others (UPs) are defined as any incident, experience or outcome that meets all of the following criteria:

- Unanticipated (in terms of nature, severity, or frequency) given (a) the research procedures that are described in the protocol-related documents, such as the IRB-approved research protocol and informed consent document; and (b) the characteristics of the subject population being studied; **and**
- Related or possibly related to participating in the research (possibly related means there is a reasonable probability that the incident, experience or outcome may have been caused by procedures involved in the research); **and**
- Suggests that the research place participants or others at a greater risk of harm (including physical, psychological, economic, or social harm) than was previously known or recognized.

Participating sites are responsible for reporting all UPs to MSK as soon as possible but within 3 calendar days of learning of the event. UPs that are SAEs should be reported to MSK via SAE Report form as per section 7.0 of this addendum. All other UPs should be reported to MSK in a memo signed by the site PI.

MSK is responsible for submitting UPs to the MSK IRB/PB according to institutional guidelines. In addition, MSK is responsible for notifying participating sites of all non-SAE UPs that may affect the sites.

### **18.0 INFORMED CONSENT PROCEDURES**

Before protocol-specified procedures are carried out, consenting professionals will explain full details of the protocol and study procedures as well as the risks involved to participants prior to their inclusion in the study. Participants will also be informed that they are free to withdraw from the study at any time. All participants must sign an IRB/PB-approved consent form indicating their consent to participate. This consent form meets the requirements of the Code of Federal Regulations and the Institutional Review Board/Privacy Board of this Center. The consent form will include the following:

1. The nature and objectives, potential risks and benefits of the intended study.
2. The length of study and the likely follow-up required.

3. Alternatives to the proposed study. (This will include available standard and investigational therapies. In addition, patients will be offered an option of supportive care for therapeutic studies.)
4. The name of the investigator(s) responsible for the protocol.
5. The right of the participant to accept or refuse study interventions/interactions and to withdraw from participation at any time.

Before any protocol-specific procedures can be carried out, the consenting professional will fully explain the aspects of patient privacy concerning research specific information. In addition to signing the IRB Informed Consent, all patients must agree to the Research Authorization component of the informed consent form.

Each participant and consenting professional will sign the consent form. The participant must receive a copy of the signed informed consent form.

## **18.1 FOR PARTICIPATING SITES**

The investigators listed on the Consenting Professionals Lists at each participating site may obtain informed consent and care for the participants according to Good Clinical Practice and protocol guidelines.

A note will be placed in the participant's medical record documenting that informed consent was obtained for this study, and that the participant acknowledges the risk of participation.

